### **Exclusion criteria**

- Patient lacks the capacity to consent to the research project (study will not utilize LAR signatures during the informed consent process)
- Weigh < 100 pounds
- BMI > 38
- Pregnancy or suspected pregnancy
- Past medical history of opioid addiction.
- Established hypersensitivity (ie allergy) to morphine.
- Acute or chronic liver disease for example cirrhosis.
- Use of any narcotics 5 days before surgery (opioids, hydrocodone, morphine, hydromorphone, fentanyl, etc).
- Undergoing bilateral total knee replacement, revision total knee arthroplasty, or any additional procedure outside of a primary total knee arthroplasty.
- Unable to get general and spinal anesthesia.
- Same-day discharge on day of surgery.

We will access the following data from medical records (Epic) including PHI:

- MRN, date of surgery, age, gender, past medical history, height, weight, BMI, laterality, pre-operative ROM, pre-operative pain VAS, intra-operative tourniquet pressure, procedure duration, and medications received during hospital stay.

Post-operatively we will ask study patients in both groups to complete a post-op symptom journal that will collect the following information in the interim before the patient's standard 2 week post op appointment with [name], [name], or [name]:

- Record daily pain levels using a validated pain scale for 14 days post op.
- Record daily pain medication use for days 14 post-op.
- Record daily nausea levels using a validated scale as well as recording bowel movements and any instances of emesis for 7 days post op.

Additionally, the tourniquet pressure intra-op will be standardized to 275 mmHg across all 3 providers on the research team (Drs. [name], [name], and [name]). This falls within the normal standard of care for all 3 providers for their total knee arthroplasty patients. However, it has been shown in the literature that tourniquet pressure can influence acute post-operative muscle quality including increased pro-inflammatory cytokines. Therefore, to limit outside factors on post-operative inflammatory marker levels as well as post-operative rehabilitative outcomes the research team will use the same tourniquet pressure for all study patients. This does not reflect an elevation in risk for study patients since 275 mmHg falls within range of standard of care for total knee arthroplasty patients for all 3 providers.

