### **Baseline and Post-op Blood Samples:**

Systemic sample – Blood draws will only be done with [name] patients that decide to participate in the study if they are the first or second case of the day. Three blood draws will be taken in these patients including just after induction of anesthesia, 15 minutes after the tourniquet is released, and 10 hours post op. The 10hr post-op blood draw timing will be based on the timing of the intraosseous injection. Serum samples will be used to measure inflammatory cytokines IL-6 and IL-8, and expression of CD11a, CD11b, CD11c, and CD18 as well as the systemic level of morphine present in the blood. Only these specific study patients will be having blood draws done due to the 10 hr post-op draw needing to be processed within 30 minutes of the draw. Blood samples will be collected in EDTA glass tubes by Houston Methodist nursing staff or a qualified member of the research team (eg. physician, fellow, or resident). Up to 10 ml of blood will be collected per time point.

For our primary outcome variable of VAS recorded pain, power analysis was performed using JMP statistics software utilizing data extracted from prior work done on the average VAS-Pain scores for TKA patients.

The statistical model for this investigation to be utilized in this investigation is a 2(Treatment) x 2(Time-point) mixed model analysis of covariance with repeated measures, co-varied on pre-operative VAS scores recorded on the day of surgery. Although there will be several days of VAS recorded out to 14-days post-surgery, the statistical question for pairwise comparisons will be to determine (1) how pain recorded on each subsequent day compares back to initial baseline (pre-operative) values within each group (treatment vs control) and (2) how each group compares to each other at the same measurement time-point. Therefore, each subsequent day will be modeled separately against the baseline value.

From the reference cited above, the 3-day average VAS score immediately following TKA was 3.2 cm (standard deviation, 2.0cm). The minimum detectable change (MDC) to detect will be set at 1.6cm as described in the literature.

The primary hypotheses of the study is that the treatment group will experience a reduction in post-operative pain compared to the control group. Based on the previous literature listed above, for a power analysis of 2 groups across 2 time-points, to detect a MDC of 1.6cm at a statistical

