power of 0.9 ( $\alpha=0.05$ ), we will require a total of 35 patients per group (total of 140 observations). To account for a potential patient dropout rate of ~20%, we will aim to recruit 42 patients per group for a total of 84 patients.

The aforementioned statistical analysis will be performed at the end of each year to evaluate the efficacy of the intervention and to identify potential outliers in the data or any possible errors in data entry. Yearly analysis using the same statistical modeling will also be performed for our secondary outcome measures (tissue biomarkers) in order to prevent potential tissue sample and biochemical reagent degradation over time and to confirm the accuracy of the tissue analysis procedure performed.

Additionally, the study will stop recruiting if adverse effects is significantly different between the two treatment groups, or greater than the previously specified risks listed within the informed consent and protocol or if a new unanticipated adverse effect is discovered. Recruitment will be suspended if there are 5 similar adverse events in a row. The most serious risks include respiratory depression, apnea, circulatory depression, respiratory arrest, shock, and cardiac arrest. These risks are <1% of the population. More frequent adverse effects include sedation, lightheadedness, dizziness, nausea, vomiting, and constipation. Patients will be monitored for these side effects in the immediate post-operative period.

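### The biomarkers inherit the pain model, so each marker's own post-induction value is not named as a covariate and Aim 2 loses precision of unknown size

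*Combined protocol and SAP*

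**What the plan says.** All the relevant text is in section 3 of the combined protocol and SAP, under Baseline and Post-op Blood Samples and in the statistical paragraphs that follow.

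- **Model.** The pain analysis is "a 2(Treatment) x 2(Time-point) mixed model analysis of covariance with repeated measures, co-varied on pre-operative VAS scores recorded on the day of surgery". No other model is defined anywhere.
- **How time enters.** For pain, "each subsequent day will be modeled separately against the baseline value". The stated comparisons are each day against baseline within a group, and group against group at the same time-point.
- **Biomarkers.** "Yearly analysis using the same statistical modeling will also be performed for our secondary outcome measures (tissue biomarkers"). No covariate specific to the biomarkers is named.
- **Blood draws.** They are taken "just after induction of anesthesia, 15 minutes after the tourniquet is released, and 10 hours post op", and used to measure IL-6, IL-8, CD11a, CD11b, CD11c and CD18, as well as morphine. Only participants who are the first or second case of the day are sampled. The expected number is not given.

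Aim 2 in section 1 is a fall in systemic inflammatory markers. It names neither a marker nor a time.

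**The concern.** In the pain analysis, pre-operative VAS is the outcome's own baseline, and adjusting for it is sound. Carried over unchanged to IL-6 or CD11b, it is the baseline of a different variable, and the protocol gives no reason why it should predict an inflammatory marker. Meanwhile the plan takes a post-induction sample whose marker values are the natural covariates, and never gives them that role.

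At stake is the precision of Aim 2. The aim rests on a subset of 84 patients, and own-baseline adjustment would cost no further data. There is also a question of pre-specification: the biomarkers are to be analysed yearly, so an unsettled covariate could end up being chosen with data in hand.

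**Working it through.** **The plan's own figure.** The only sample size in the documents is for pain: 35 per group, from a difference of 1.6 cm, SD 2.0 cm, power 0.9 and alpha 0.05 (two-sided assumed, since sidedness is not stated). The normal formula gives 2 × (1.960 + 1.282)² × 2.0² / 1.6² = 2 × 10.51 × 1.5625 = 32.8, so 33 per group; the two-sample t version gives 34. The stated 35 is thus reproduced to within two patients. It says nothing about the biomarkers, for which no SD, correlation, effect size, subset size or power is given.

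**Inputs for the comparison.** Let r be the within-arm correlation between a marker's post-induction value and a later value. It is not in the documents; 0.3 to 0.7 is an assumption, and r may differ by marker and by draw. Further assumptions are equal variance at the two times, randomised arms, and VAS explaining none of the marker variance. The degree of freedom used by the covariate is the same whether it is VAS or the marker's own baseline, so it cancels.

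**Variance of the treatment effect**, on a scale where an unadjusted comparison of later values is 1:

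- ANCOVA on the marker's own baseline: 1 − r²
- comparison of later values, own baseline not used: 1
- change from baseline, which is the treatment-by-time contrast when the post-induction draw is one of the two time-points: 2(1 − r)

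The ratios to own-baseline ANCOVA are therefore 1/(1 − r²) for later values and 2(1 − r)/(1 − r²) = 2/(1 + r) for change.

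| r (assumed) | Later values | Change from baseline |
|---|---|---|
| 0.3 | 1/0.91 = 1.10 | 2/1.3 = 1.54 |
| 0.5 | 1/0.75 = 1.33 | 2/1.5 = 1.33 |
| 0.7 | 1/0.51 = 1.96 | 2/1.7 = 1.18 |

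Confidence intervals widen by the square roots: 1.05, 1.15 and 1.40 for later values, and 1.24, 1.15 and 1.08 for change. For any r strictly between 0 and 1 both ratios exceed 1. The direction of the loss is therefore fixed, while its size depends on r and on which contrast is reported. The text permits both contrasts: the pain plan asks for comparison with baseline and also for group comparison at the same time-point.

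**The case against.** The strongest reply is that using the same modelling can mean the same type of model with each outcome's own baseline as covariate. VAS is the baseline of the pain outcome, and with the post-induction value as covariate the two later draws fit a two-by-two layout exactly. On that reading nothing is lost. It is a fair reading, but the covariate written down is VAS and no sentence substitutes another. What stands is that the biomarker covariate is not settled, and the literal text settles it badly.

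A second reply is that the quoted sentence speaks of tissue biomarkers, whereas the draws are blood. The link to the serum markers is indeed an inference. If the sentence does not cover them, the plan states no model at all for Aim 2, and the same fix is needed.

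Several stronger conclusions are tempting and are not supported:

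- *The baseline draw is ignored.* Modelling each later assessment against baseline can bring it in as a response time-point. A change contrast then uses it and deals with chance imbalance, though less efficiently than ANCOVA.
- *The loss is always 1.33 to 1.96 times.* That range belongs to the later-value comparison at r of 0.5 to 0.7. It omits low r (1.10 at 0.3) and does not apply to the change contrast.
- *A detectable difference can be quoted.* An equal split over three surgeons would give 84/3 = 28 patients, 14 per arm, but nothing in the documents fixes one surgeon's share or the effect of the case-order rule.
- *The false-positive risk is 46%.* Six markers at two later draws give 1 − 0.95¹² = 0.46 only if the tests are independent, which is a worst case, and multiplicity is a separate matter from the covariate.
- *ROM, KOOS JR and PROMIS are also adjusted for VAS.* The sentence extends the model to the tissue biomarkers only.

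**Conclusion.** The point holds as an omission that lowers precision. As written, the biomarker model has pain VAS as its only named covariate, and each marker's post-induction value is at most a response. Relative to own-baseline ANCOVA, the variance of the treatment effect is 1.54 to 1.18 times for change from baseline and 1.10 to 1.96 times for later values, as r runs from 0.3 to 0.7. These figures rest on the assumed r, equal variances over time, and VAS being unrelated to the markers. At r = 0 the later-value comparison loses nothing.

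The effect on power cannot be stated, because the subset size is missing. The matter concerns a secondary aim for which no power is claimed, and it leaves the primary pain analysis untouched. It is worth correcting because the remedy uses data that the plan already collects.

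**What to change.** Replace the reference to the same modelling, for the six inflammatory serum markers, with wording such as: *For each marker, the values at 15 minutes after tourniquet release and at 10 hours will be analysed in a repeated-measures model with treatment, time and treatment-by-time, and with the post-induction value of the same marker as covariate in place of pre-operative VAS. Values will be log-transformed if skewed.* The same edit should say that the sentence now headed by tissue biomarkers refers to the serum markers, if that is what is meant.

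This costs only analysis wording: the post-induction draw is already scheduled, and no visit, sample or procedure changes.

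Optionally, before any yearly analysis, name one marker and one time as the test of Aim 2 and label the rest exploratory. The small downside is that the other markers then cannot confirm Aim 2.

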## 3. Study Design

This study is a double-blind randomized controlled trial with two arms. The control group will receive an intraosseous (IO) injection of antibiotics as per [name], [name], and [name] standard of care for primary TKA patients. The experimental group will receive an IO injection of antibiotics mixed with 10 mg of morphine. A research coordinator on the study team will inform the circulator nurse present in the OR during the study patient's case about which group (morphine or no morphine) the patient is in. The circulator nurse will then be instructed to place morphine into the surgical field during the mixing process of the intraosseous solution without notifying the surgeon to ensure the double blind. Patient's post-operative pain levels, pain medication consumption, side effects to pain medications, and range of motion will be recorded for 14 days following surgery.

Patient outcomes will also include pain levels, post-operative pain medication use, and post-operative ROM.

The anticipated total number of participants is 84 with 42 patients being in each group. The maximum number of subjects who will be enrolled is 84 patients (i.e. give consent to participate) at this site.

Participants will be randomized into either the control group or the experimental group by an excel-based software program.

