This study will not require the patient to attend any additional study visits. The expected amount of time the patient for the patient to complete all study related items including filling out the symptom journal and answered pre/post-op surveys is approximately 90 minutes. The patient will participate in the study for a total of 52 weeks. The anticipated duration to enroll all study subjects is 18 months. The estimated date for the investigators to complete primary analyses is 2.5 years following the initiation of the study.

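### Yearly biomarker rounds, implied by the plan, are analysed with the pain model, which has neither an assay-run term nor the marker's own baseline, so the same-time-point comparison for Aim 2 may lose precision

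*Combined protocol and SAP*

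**What the plan says.** The statistical text is in section 3, under the heading on baseline and post-operative blood samples. For pain it specifies a "2(Treatment) x 2(Time-point) mixed model analysis of covariance with repeated measures, co-varied on pre-operative VAS scores recorded on the day of surgery". One of its two pairwise questions is "how each group compares to each other at the same measurement time-point"; the other compares each day with baseline within a group.

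The biomarkers get no model of their own: "Yearly analysis using the same statistical modeling will also be performed for our secondary outcome measures (tissue biomarkers"). The reason given for the yearly timing is "in order to prevent potential tissue sample and biochemical reagent degradation over time and to confirm the accuracy of the tissue analysis procedure performed".

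The samples that this section describes are blood: "Serum samples will be used to measure inflammatory cytokines IL-6 and IL-8, and expression of CD11a, CD11b, CD11c, and CD18". They come only from one provider's first- and second-case patients, with draws after induction, 15 minutes after tourniquet release and 10 hours post-operatively. The number of such patients is not given.

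On timing, Study Intervention says: "The anticipated duration to enroll all study subjects is 18 months". On allocation, section 3 says: "Participants will be randomized into either the control group or the experimental group by an excel-based software program". It mentions no blocking by calendar time.

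**The concern.** The plan treats ageing of samples and reagents, and the accuracy of the assay procedure, as reasons to work year by year. If assays are run that way, marker levels from different rounds may not be on exactly the same scale. The model carried over from pain cannot absorb such a difference. It has treatment, time-point and a pain score, and the pain score says nothing about assay level.

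A shift between rounds would then sit in the residual variation of the arm comparison at each draw. Where the arms happen to be unequally spread over the rounds, part of the shift would also appear as a difference between arms. Aim 2 depends on these markers, the sampled subset is likely to be small, and no power is stated for it, so avoidable noise matters.

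**Working it through.** **The plan's own figure.** The only sample-size figure concerns pain. With a difference of 1.6 cm, SD 2.0 cm, two-sided alpha 0.05 (sidedness assumed) and power 0.9, n = 2 × (1.96 + 1.28)² × 2.0² / 1.6² = 33 per group, or 34 by the t distribution. The stated 35 is consistent with this (power 0.91 by t). There is no corresponding figure for the biomarkers.

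**From the documents.** Enrolment of 18 months gives 12/18 = 67% of patients in year 1 and 33% in year 2 if accrual is even. The model terms and the three draws are as described above.

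**Assumed, because the documents are silent.** 20 to 40 sampled patients in total; equal arms, allocated without regard to round; two rounds split 2/3 to 1/3; an additive shift between rounds of δ within-run SD (this SD includes the spread between patients); correlation 0.5 between a marker's baseline and its post-operative value.

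**Added variance.** An unmodelled shift adds (2/3)(1/3)δ² = 0.22δ² to a within-run variance of 1. That is +5.6% at δ = 0.5, +22% at 1.0 and +50% at 1.5.

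**Chance imbalance.** With 28 patients, 9 fall in round 2. If k of them are in one arm of 14, the arms differ in round-2 share by |2k − 9|/14. Under the hypergeometric distribution this is 20 points or more in about 42% of trials. The same calculation gives about 35% with 20 patients (7 in round 2) and 18% with 40 (13 in round 2). A 20-point imbalance with δ = 1.0 moves the estimate by 0.20 × 1.0 = 0.20 SD, in either direction.

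**Power at one post-operative draw.** Simulation with 28 patients in total and an effect set to give 80% power with no shift:

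| Shift (SD) | No run term | Run term | Gain | Marker baseline, no run term | Marker baseline and run term | Gain |
|---|---|---|---|---|---|---|
| 0 | 80% | 79% | −1 | 88% | 86% | −2 |
| 0.5 | 78% | 79% | +1 | 88% | 88% | 0 |
| 1.0 | 71% | 78% | +7 | 86% | 87% | +1 |
| 1.5 | 62% | 77% | +15 | 85% | 87% | +2 |

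The marker-baseline columns assume that a patient's baseline and post-operative samples are assayed in the same run.

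**Change from baseline and type I error.** A separate simulation used 20 patients per arm and an effect of 0.8 SD. For shifts of 0, 0.5, 1 and 2 SD, power at a single draw without a run term was 0.69, 0.68, 0.61 and 0.42. Change from a same-run baseline, also without a run term, stayed at 0.68 to 0.70. Over 10 to 30 patients per arm, type I error without a run term was 0.044 to 0.059.

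**The case against.** The strongest reply is that yearly assay rounds are not in the text. It speaks of yearly analysis and of tissue biomarkers, and it mentions neither runs nor lots. The revision history records that bone and soft-tissue collection was dropped, so the sentence may be left over from it. It stands that the rounds, and their application to blood, are inferred. The inference is still the natural one, because only running the assays can forestall degradation of samples and reagents.

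A reader might infer that samples are processed once a year. The documents do not support that: the 10-hour draw has to be processed within 30 minutes. Nor do they show that any shift occurs; confirming assay accuracy is itself one purpose of the yearly work. Shifts of 1.0 to 1.5 SD are large, and nothing in the documents points to them.

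A reader might also suppose that one patient's draws fall in different rounds. All three are taken from induction to about 10 hours after the injection, so yearly rounds would normally keep them together, although no rule says so.

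Finally, the design already has a post-induction baseline, and an additive shift cancels in change from baseline and in treatment-by-time contrasts when samples share a run. That stands, and it limits the point to the comparison of arms at the same time-point. That comparison is one the plan says it will make, and the covariate it adjusts for is pain, not the marker's baseline.

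**Conclusion.** The concern holds in a limited form. The plan implies at least two assay rounds and reuses a model with no run term and no marker baseline. If levels shift between rounds, the same-time-point comparison for Aim 2 loses precision and is exposed to chance imbalance.

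It would be tempting to call this a biased treatment effect. Under randomisation the imbalance is random error, the simulated type I error stays near 0.05, and so the cost is precision.

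The size rests on assumptions about subset size, split and shift. With 28 patients the loss that a run term recovers is negligible at 0.5 SD and reaches 7 to 15 points at 1.0 to 1.5 SD. Most of it disappears if the same-run marker baseline is a covariate, and that covariate does more for power than the run term does. The priority is minor to moderate.

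**What to change.** In the statistical text of section 3:

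1. Replace the reference to tissue biomarkers with the blood markers that the section lists, and state the assay schedule.
2. Assay all three draws from one patient in the same run, with the same reagent lot where the assay allows, and include patients from both arms in every run.
3. Model each inflammatory marker with its own post-induction baseline as covariate in place of pre-operative VAS, and with assay run (or year) as a fixed factor.

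The yearly rounds can stay. The change takes a few sentences in the analysis plan and the laboratory instructions, with no extra samples or patients. The run factor uses one or two degrees of freedom, which costs about 1 to 3 points of power if there is no shift. It should be settled before the first yearly look, so that the choice of adjustment does not follow the data.

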## 1. Purpose of the Study / Objectives

The purpose of this study is to determine if IO morphine decreases pain, inflammatory markers, and post-operative opioid use in total knee arthroplasty (TKA) patients.

- Aim 1: IO morphine will significantly reduce patient pain in the post-operative period after primary TKA.
  - Sub aim: IO morphine will cause significantly higher levels of morphine within the joint compared to current standard of care.
- Aim 2: IO morphine will decrease systemic inflammatory markers in the post-operative period after primary TKA.
- Aim 3: IO morphine will result in significantly less post-operative oral opioid use, and achieve superior outcomes such as increased range of motion (ROM).

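### The between-group adverse-effect rule has no direction, so recruitment could stop because IO morphine causes fewer adverse effects

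*Combined protocol and SAP*

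**What the plan says.** The recruitment rules follow the sample-size text in section 3 (Study Design), under the blood-sample subheading. There are four.

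- A between-group rule: "the study will stop recruiting if adverse effects is significantly different between the two treatment groups".
- A reference-risk rule, which stops recruitment if adverse effects are "or greater than the previously specified risks listed within the informed consent and protocol".
- A novelty rule, which stops recruitment "if a new unanticipated adverse effect is discovered".
- A run rule, with suspension as its action: "Recruitment will be suspended if there are 5 similar adverse events in a row".

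The same paragraph names six serious risks and says of them "These risks are <1% of the population". It then lists six commoner ones: "More frequent adverse effects include sedation, lightheadedness, dizziness, nausea, vomiting, and constipation". No rate is given for these six.

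Two other sections bear on the between-group rule. Aim 3 in section 1 states that "IO morphine will result in significantly less post-operative oral opioid use". Section 2 (Background) includes nausea, vomiting and constipation among the side effects of oral opioids.

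Section 13 (Data Safety Plan) adds only that study clinicians monitor the trial and that interim analysis is yearly. Section 8 (Withdrawal of Subjects) answers an allergic or negative reaction to the injection with a report to the IRB and removal of that patient, and does not mention recruitment.

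**The concern.** A safety rule that halts recruitment is meant to protect patients from harm by the experimental treatment. This one is worded as a difference, so a significant deficit of adverse effects with morphine meets it as fully as a significant excess does.

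The trial's own hypothesis makes the favourable direction a real possibility. If IO morphine spares oral opioids, the control arm takes more of them and may have more of the side effects that the Background attributes to them. The symptom journal records nausea, emesis and bowel movements in both arms, so the data that could trigger the rule will be collected.

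Stopping for that reason would leave the pain comparison below its planned size. The missing endpoint, test and level add to the problem, because the chance of stopping on noise depends heavily on how many adverse effects are compared and how.

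**Working it through.** **Inputs from the protocol.** SD 2.0 cm, difference 1.6 cm, power 0.9, alpha 0.05, 35 evaluable per group, 42 per group recruited (section 3); enrolment over 18 months (Study Intervention); yearly analyses (sections 3 and 13).

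**Assumptions.** Uniform accrual; adverse effects compared on the yearly schedule; two-sided 0.05 for adverse effects (the protocol states 0.05 only for the pain power analysis); the adverse-effect rates below.

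**1. The plan's sample size.** n = 2(1.960 + 1.282)² × 2.0² / 1.6² = 32.8, so 33 per group; the two-sample t version gives 34. The stated 35 is consistent with this. 35 × 1.2 = 42.

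**2. When the rule can act.** With 18 months of enrolment, the only yearly look during recruitment is at month 12. Patients by then: 84 × 12/18 = 56, or 28 per arm. At 42 per arm enrolment is complete and a recruitment stop has no effect, so 28 per arm is the relevant size.

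**3. Chance of stopping in morphine's favour.** Let X ~ Bin(28, p_morphine) and Y ~ Bin(28, p_control). Sum P(X = x)P(Y = y) over all pairs with x < y and two-sided p < 0.05.

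| Assumed rate, morphine v control | Fisher | Chi-square |
|---|---|---|
| 40% v 50% | 0.07 | 0.11 |
| 30% v 50% | 0.24 | 0.33 |
| 20% v 50% | 0.57 | 0.67 |

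**4. What such a stop costs.** With 28 per arm and standardised difference 1.6/2.0 = 0.8, a two-sided two-sample t-test has power about 0.84. If 20% drop out, 28 × 0.8 = 22.4, so 22 per arm, and power is about 0.74. The target was 0.9.

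**5. Why the comparison must be named.** One overall comparison at one look has a false-stop chance at the nominal 5%. Six separate 0.05 tests give 1 − 0.95⁶ = 0.265 if independent. Simulation at 28 per arm, with null rates of 20% to 40% and correlation between effects from 0 to 0.5, gave 0.25 to 0.28 (chi-square) or 0.13 to 0.14 (Fisher). By symmetry about half of these false stops would favour morphine.

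**6. The other triggers, for one type of serious event.**

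- Reference-risk rule: 1/84 = 1.2% and 1/42 = 2.4%. The first event already exceeds 1% if the crude trial proportion is the comparison.
- Run rule: the probability of five consecutive patients with the event among 84, at a 1% rate, is 7.9 × 10⁻⁹ (Markov chain on the current run length).
- Between-group rule with Fisher: 5 v 0 of 42 gives p = 0.055 and 6 v 0 gives p = 0.026, so six events to none are needed.

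**The case against.** The strongest reply is that anyone running the trial would read the rule as a guard against harm, and the study clinicians would not halt recruitment over fewer side effects. That may be so, but no section says it.

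It can also be said that the favourable direction is uncertain: morphine itself is listed as causing nausea, vomiting and constipation, so the experimental arm could have more of them. This stands. The argument is only that a control-arm excess is plausible under Aim 3, and the probabilities in the table are conditional on assumed rates.

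Several stronger readings are tempting, and the documents do not support them.

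- **Six separate uncorrected tests.** The text speaks of adverse effects as a whole and may mean one overall comparison. The 26% figure is what one reading would give. Leaving a safety trigger unadjusted is also a defensible cautious choice.
- **Inflation over repeated looks.** On a yearly schedule there is only one look during recruitment. The protocol does not say that adverse effects are compared more often.
- **The run rule suspends readily for expected effects.** No rate for these is documented. For one effect among 84 patients, a run of five has probability 0.02 at a 20% rate, 0.13 at 30% and 0.40 at 40%, so the claim depends wholly on the assumed rate. Counting runs within arm would barely help: 0.388 against 0.401 at a 40% rate.
- **The triggers contradict each other.** They are alternatives with different actions, stop or suspend, and meeting any one suffices. They differ greatly in sensitivity, which is a matter for reconciliation. The reference-risk rule also refers to risks listed in the consent form, which is not available here.

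**Conclusion.** The between-group rule lacks a direction, and followed literally it could end recruitment because IO morphine reduces adverse effects. This follows from the text and needs no assumption.

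Its size does need assumptions. At about 28 per arm, with one effect at 30% v 50% and a two-sided 0.05 test, the probability is 0.24 to 0.33; across the assumed rates shown it runs from 0.07 to 0.67. A stop there would lower power for pain from 0.9 to about 0.84, or about 0.74 with 20% dropout. These figures rest on uniform accrual and a yearly comparison, neither of which the protocol states for adverse effects.

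The absence of a named comparison, test and level is a second, related gap. The uneven sensitivity of the remaining triggers to serious events needs clarifying but is not a demonstrated error. The point should be corrected and is inexpensive to correct.

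**What to change.** In section 3, reword the between-group trigger so that it fires only on a significant excess of adverse effects in the IO morphine group. In the same sentence, name the single adverse-event comparison it uses, the test and the level. One overall comparison keeps the false-stop chance at the nominal level without a multiplicity correction.

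The cost is protocol wording. The downside is that an excess in the control arm would no longer stop recruitment automatically.

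Separately, the sponsor and the safety reviewers should reconcile the run rule, the reference-risk rule and section 8. They should say what counts as similar and in a row, which reference rates apply and how they are compared with trial data, and which rule takes precedence. No replacement threshold is proposed here, and the freedom to suspend at any time for a serious or unanticipated event should stay unchanged.
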